## 5.2.1.6 Dose Interruptions

If a subject misses a dose of Zepatier and it is less than 8 hours before the next dose, the missed dose should be skipped and the normal dosing schedule resumed. Subjects should not double the next dose in order to compensate for what has been missed.

If for any reason Zepatier needs to be interrupted it can be interrupted for up to 3 days. If Zepatier is interrupted for more than 3 days, consult Merck for that patient. RBV is not to be taken as monotherapy in the absence of Zepatier.

If pembrolizumab treatment is interrupted then maintain the subject on Zepatier ( $\pm$ RBV) unless due to severe liver toxicity. No dosage adjustment of Zepatier is recommended in patients with mild hepatic impairment (Child-Pugh A). Zepatier is contraindicated in patients with moderate hepatic impairment (Child-Pugh B) or severe hepatic impairment (Child-Pugh C).

If a subject misses a dose of RBV, then they should take the missed dose as soon as possible with food during the same day. If an entire day has gone by, then these missed doses should be skipped, and the normal dosing schedule should be resumed. Subjects should not double the next dose in order to "make up" what has been missed.

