### **5.2.1.4 Zepatier Dose Modification (Escalation/Titration/Other)**

Dose modification of Zepatier is not permitted with the exception of hepatic events, SAEs, or laboratory abnormalities.

During clinical trials with Zepatier with or without RBV, 1% of subjects experienced elevations of ALT from normal levels to greater than  $5 \times$  ULN, generally at or after treatment week 8. ALT elevations were typically asymptomatic and most resolved with ongoing or completion of therapy. Higher rates of late ALT elevations occurred in the following subpopulations: female sex (2% [10/608]), Asian race (2% [4/164]), and age 65 years or older (2%). For ALT elevations on Zepatier, follow recommendations in full prescribing information.

Hepatic laboratory testing should be performed prior to therapy, at treatment Week 8, and as clinically indicated. For patients receiving 16 weeks of therapy, additional hepatic laboratory testing should be performed at treatment week 12.

- Subjects should be instructed to consult their healthcare professional without delay if they have onset of fatigue, weakness, lack of appetite, nausea and vomiting, jaundice, or discolored feces.
- Consider discontinuing Zepatier if ALT levels remain persistently greater than  $10 \times$  ULN.
- Discontinue Zepatier if ALT elevation is accompanied by signs or symptoms of liver inflammation or increasing conjugated bilirubin, ALP, or INR.

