## 6.0 TRIAL FLOW CHART

### 6.1 Study Flow Chart Initial Treatment with Pembrolizumab

Trial Period:	Screening Phase	Treatment Cycles (3-Week Cycles). 1 year or treatment or 17 cycles in total.								End of Treatment	Virologic Failure – Arm B s	Post-treatment		
		1	2	3	4	5	6	7	≥8			Safety Follow-up l	Follow-Up Visits	Survival Follow-Up a
Treatment Cycle/Title:	Screening	1	2	3	4	5	6	7	≥8	DC		Safety Follow-up l	Follow-Up Visits	Survival Follow-Up a
Week (approximate)	0	3	6	9	12	15	18	21	24	At DC		30 days post last dose	Q9W post-DC	Q12W
Scheduling Window (Days) b	-28 to -1	±3	±3	±3	±3	±3	±3	±3	±3	±3	±7	±7	±7	±7
Administrative Procedures														
ICF	X													
Inclusion/exclusion criteria	X													
Demographics and medical history	X													
Prior and concomitant medication review	X	X	X	X	X	X	X	X	X	X	X			
Post-study anticancer therapy status											X	X	X	
Zepatier and Ribavirin Medication adherence		X	X	X	X	X	X	X	X					
Survival status u		X	X	X	X	X	X	X	X	X	X	X	X	X
Clinical Procedures/Assessments														
Review AEs	X	X	X	X	X	X	X	X	X	X	X	X l		
Full physical examination	X									X	X			
Directed physical examination		X	X	X	X	X	X	X	X					
Child-Pugh score	X													

Trial Period:	Screening Phase	Treatment Cycles (3-Week Cycles). 1 year or treatment or 17 cycles in total.								End of Treatment	Virologic Failure – Arm B s	Post-treatment		
		1	2	3	4	5	6	7	≥8			Safety Follow-up l	Follow-Up Visits	Survival Follow-Up a
Treatment Cycle/Title:	Screening	1	2	3	4	5	6	7	≥8	DC				
Week (approximate)	0	3	6	9	12	15	18	21	24	At DC		30 days post last dose	Q9W post-DC	Q12W
Scheduling Window (Days) b	-28 to -1	±3	±3	±3	±3	±3	±3	±3	±3	±3	±7	±7	±7	±7
Height, weight, and vital signs (T, P, RR, BP) c	X	X	X	X	X	X	X	X	X	X				
12-Lead ECG	X													
Upper endoscopy	X													
ECOG performance status	X e	X	X	X	X	X	X	X	X	X				
Pembrolizumab administration		X b	X	X	X	X	X	X	X					
LOCAL Laboratory Assessments														
Pregnancy test d	X	X	X	X	X	X	X	X	X	X		X		
PT/INR and aPTT	X e		X	X	X	X	X	X	X	X		X		
CBC with differential f	X e		X	X	X	X	X	X	X	X		X		
Chemistry panel f	X e		X	X	X	X	X	X	X	X		X		
Liver panel g,t	X e		X	X	X	X	X	X	X	X		X		

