Urinalysis h	X e		X		X		X		X	X				
T3, FT4, and TSH h	X e		X	X	X		X		X	X		X		
AFP m	X e	X		X			X			X		X		
C-Reactive protein		X	X			X				X				
Fibrotest	X													
APRI	X													
Coagulation														
Serum IGF-1	X p			X			X			X				

Trial Period:	Screening Phase	Treatment Cycles (3-Week Cycles). 1 year or treatment or 17 cycles in total.									End of Treatment	Virologic Failure – Arm B s	Post-treatment		
		1	2	3	4	5	6	7	≥8	DC			Safety Follow-up l	Follow-Up Visits	Survival Follow-Up a
Treatment Cycle/Title:	Screening									DC					
Week (approximate)	0	3	6	9	12	15	18	21	24	At DC		30 days post last dose	Q9W post-DC	Q12W	
Scheduling Window (Days) b	-28 to -1	±3	±3	±3	±3	±3	±3	±3	±3	±3	±7	±7	±7	±7	
Child-Turcotte-Pugh (CTP) Calculation	X														
Viral testing															
HCV Ab	X														
HCV genotype Arm B	X														
HCV viral load q, r Arm B	X	X	X	X	X	X	X	X	X	X	X	X			
If (1) HBV+ or (2) anti-HBc+ and HBsAg- and viral load-negative:															
Anti-HBc (total and IgM), anti-HBs,	X														
HBsAg and HBV viral load m	X	X	X	X	X	X	X	X	X			X			
Anti-HBc (total), anti-HBe, anti-HBs, and HBeAg m	X				X				X			X			
Plasma for HCV viral resistance testing Arm B r	X	X r									X s				
CENTRAL Laboratory Assessments															
Blood for genetic analysis k		X													
Whole blood for biomarker studies (serum and plasma) k	X	X	X							X					
Whole blood for correlative studies (RNA and DNA) k	X	X	X							X					

Trial Period:	Screening Phase	Treatment Cycles (3-Week Cycles). 1 year or treatment or 17 cycles in total.								End of Treatment	Virologic Failure – Arm B s	Post-treatment		
		1	2	3	4	5	6	7	≥8			Safety Follow-up l	Follow-Up Visits	Survival Follow-Up a
Treatment Cycle/Title:	Screening	1	2	3	4	5	6	7	≥8	DC				
Week (approximate)	0	3	6	9	12	15	18	21	24	At DC		30 days post last dose	Q9W post-DC	Q12W
Scheduling Window (Days) b	-28 to -1	±3	±3	±3	±3	±3	±3	±3	±3	±3	±7	±7	±7	±7
Newly Obtained Tissue Collection k	X		X							X				
Efficacy Measurements														
Tumor imaging i	X j,n	X o		X		X				X		X	X	

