Abbreviations: AEs = adverse events; AFP = alpha fetoprotein; APRI = aspartate aminotransferase:platelet ratio index; aPTT = activated partial thromboplastin time; BP = blood pressure; CBC = complete blood count; DC = discontinuation; ECG = electrocardiogram; ECOG = Eastern Cooperative Oncology Group; FT4 = free thyroxine; HBV = hepatitis B virus; HBcAg = hepatitis B core antigen; HBsAb = anti-HBsAg antibody; HBsAg = hepatitis B surface antigen; HCV = hepatitis C virus; ICF = informed consent form; IGF-1 = insulin-like growth factor-1; INR = international normalized ratio; P = pulse; Q3W = every 3 weeks; Q9W = every 9 weeks; Q12W = every 12 weeks; RR = respiratory rate; T = temperature; PT = prothrombin time; T3 = triiodothyronine; TSH = thyroid-stimulating hormone.

- In subjects that experience site-assessed PD or start a new anti-cancer therapy, contact should be made (eg; by telephone) Q12W to assess for survival status.
- Cycle 1 treatment must be given within 3 days of allocation. The window for each visit is ±3 days until the end of treatment and ±7 days during follow-up.
- Height will be measured at screening only. For women of reproductive potential, a urine or serum pregnancy test should be performed within 72 hours prior to Day 1 of each treatment cycle and 30 days post treatment.
- A serum test can be done if urine is not appropriate. Additionally, if urine test is positive or is not evaluable, a serum test is required. Subjects must be excluded/discontinued in the event of a positive test results Monthly pregnancy testing should be conducted as per local regulations where applicable.
- ECOG Performance Status and laboratory tests for screening and determining eligibility are to be performed within 7 days and 10 days, respectively, prior to the first dose of trial treatment.
- CBC with differential and chemistry to be performed every cycle
- Liver panel (albumin, ALT, AST, total and direct bilirubin, and alkaline phosphatase) to be performed at screening and then every week for the first 2 cycles followed by every cycle starting at cycle 3. Liver panel will also be done at discontinuation and safety follow-up.

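### Zepatier is contraindicated from Child-Pugh class B, but the score is scheduled only at screening and no written trigger acts on a class B reached through albumin or PT without a hepatic ECI

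*Combined protocol and SAP*

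**What the plan says.** Section 5.2.1.6 says that "Zepatier is contraindicated in patients with moderate hepatic impairment (Child-Pugh B) or severe hepatic impairment (Child-Pugh C". It attaches no assessment time and no action to that sentence. The same section says "If pembrolizumab treatment is interrupted then maintain the subject on Zepatier", with an exception where severe liver toxicity is the reason; that exception is not defined by Child-Pugh class.

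In the Section 6.1 flow chart, the rows "Child-Pugh score" and "Child-Turcotte-Pugh (CTP) Calculation" are each marked once, in the screening column. Most of the ingredients are collected on treatment. The footnote reads "Liver panel (albumin, ALT, AST, total and direct bilirubin, and alkaline phosphatase) to be performed at screening", then weekly for two cycles and every cycle from cycle 3. PT/INR is marked from cycle 2 onwards.

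Section 5.2.1.4 says "Dose modification of Zepatier is not permitted with the exception of hepatic events, SAEs, or laboratory abnormalities", without a threshold. Its mandatory stop is "Discontinue Zepatier if ALT elevation is accompanied by signs or symptoms of liver inflammation or increasing conjugated bilirubin, ALP, or INR". Its optional stop is for ALT persistently above 10 × ULN.

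Section 5.2.1.3 defines the hepatic ECIs by ALT, AST, total bilirubin or clinical decompensation, and the required hold names pembrolizumab. After such an ECI, permanent discontinuation applies at 9 points or more, among other criteria. The word used there is Therapy, and no drug is named. The parts on immune-related hepatitis and on other hepatic events stop treatment at class C.

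**The concern.** The level at which the protocol contraindicates the drug (7 points) is lower than every on-treatment Child-Pugh threshold at which it instructs a stop (9 points after an ECI, or class C). The other hepatic triggers use ALT, AST, bilirubin or clinical decompensation. Albumin and PT are Child-Pugh items, but neither sets off a rule on its own; INR counts in the Zepatier stop rule only alongside an ALT elevation.

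What is at stake is subject safety and consistent handling. A team that follows the schedule and the written thresholds can leave an Arm B subject on a contraindicated drug because nobody was prompted to calculate the score. Section 5.2.1.3 itself warns that HCC subjects can develop hepatic laboratory abnormalities with or without clinical decompensation.

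**Working it through.** The plan states no figure on this point, so there is none to reproduce. The check sets the rules side by side, then counts which scores they reach.

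**1. Rules and their triggers**

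| Section | Trigger | Acts on |
|---|---|---|
| 5.2.1.6 | Class B or C (7 points or more) | Zepatier; no assessment time, no stated action |
| 5.2.1.4 | ALT elevation, alone or with other signs | Zepatier |
| 5.2.1.3, ECI list | ALT, AST, bilirubin, clinical decompensation | Pembrolizumab hold |
| 5.2.1.3, permanent discontinuation | 9 points or more, and other criteria, in ECI subjects | Therapy, drug not named |
| 5.2.1.3, immune-related hepatitis and other hepatic events | Class C | Treatment |

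**2. Inputs for the score** (Section 12.5, Tables 21 to 23)

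- Classes: A is 5–6, B is 7–9, C is above 9.
- Bilirubin, albumin and PT score 1 to 3 points each.
- Ascites and encephalopathy are set to 1 point each. Section 5.1.3 excludes both at entry when clinically apparent, and their onset is an ECI.
- Score = bilirubin + albumin + PT + 1 + 1.

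Albumin below 2.8 g/dL with everything else at 1 point gives 1 + 3 + 1 + 1 + 1 = 7, class B. A subject entering at 6 needs only one further category step.

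**3. Laboratory-only states that fire no bilirubin ECI**

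- Bilirubin at 1 point (below 2 mg/dL): score = 3 + albumin + PT, 9 states.
- Bilirubin at 2 points: taken for a baseline of 1.5 to 2.0 mg/dL (Section 5.1.3 excludes above 2.0) and a value from 2.0 to below 3.0. The ECI needs at least 2 × baseline, so 2 × 1.5 = 3.0 at the lowest, or a value above 3.0. Score = 4 + albumin + PT, 9 states.
- Bilirubin at 3 points (above 3 mg/dL) always fires the ECI and is left out.

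| Score | Bilirubin 1 point | Bilirubin 2 points | Total |
|---|---|---|---|
| 5–6 (A) | 3 | 1 | 4 |
| 7–8 (B) | 5 | 5 | 10 |
| 9 (B) | 1 | 2 | 3 |
| 10 (C) | 0 | 1 | 1 |

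The 10 states at 7–8 points lie below every numeric stop. The 3 states at 9 points have no ECI, so the 9-point rule does not reach them either. These are reachable score states, not patient frequencies.

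**4. Number of scores under the fix**

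Assume Zepatier starts on Cycle 1 Day 1 and cycles run every 21 days. Visits after Day 1 fall on days 22, 43, 64, 85 and 106. A 12-week course (days 1–84) contains 3 of them and a 16-week course (days 1–112) contains 5. For 15 subjects: 15 × 3 = 45 and 15 × 5 = 75.

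**5. Effect on SVR12**

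One subject of 15 is 1/15 = 6.7 percentage points. A subject stopped early lowers observed SVR12 by that amount if stopping turns a success into a failure, and by 0 otherwise.

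**6. Units**

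Section 5.2.1.3 sets the ALT and AST triggers at above 500 U/L; Section 7.2.4.2 writes above 500 U/mL. Since 500 U/mL is 500,000 U/L, the second is 1,000 times higher as written.

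**The case against.** The strongest reply is that Section 5.2.1.6 already is the rule: a contraindication in a dosing section means the drug should not be given. That stands. A reader might infer that the protocol permits class B dosing, or orders it through the instruction to maintain Zepatier. The documents do not support either reading. The maintain instruction has its severe-liver-toxicity exception, Section 5.2.1.4 allows modification for laboratory abnormalities, and Section 5.6.2 (Discontinuation of Treatment) lets the investigator or Merck stop inappropriate treatment. What is missing is a scheduled score and a stated action.

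There are further safeguards. The 9-point and class C stops presuppose that someone scores on treatment. Section 7.1.3.1 requires acceptable laboratory results before each dose, Section 7.1 permits unscheduled procedures, and the flow chart marks a directed examination every cycle, although Section 7.1.2.4 makes it as clinically indicated. All of this stands, but none of it sets a class threshold. Zepatier is also a daily tablet taken at home, so review happens at visits.

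Section 5.2.1.1 leaves Zepatier dosing details to the prescribing information, which is not among the documents. It may contain an on-treatment instruction; that cannot be checked here.

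A reader might also take the class B study in Section 4.2.1.4 as reassurance. It used grazoprevir 50 mg, half the 100 mg in the tablet used here, so it does not cover continuing the full dose.

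Finally, stopping antivirals early has a virologic price on a primary endpoint of Arm B. That is fair, and it is why the stop should rest on a confirmed score with room for clinical judgement.

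**Conclusion.** The gap is real and should be fixed. An Arm B subject who reaches class B through albumin or PT, without a hepatic ECI, prompts no scheduled score and no explicit action, although the protocol contraindicates Zepatier in that class. Stopping is allowed but depends on the investigator's or sponsor's initiative.

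Two stronger inferences fail. The count of 10 in 18 states does not show that the event is likely: it counts score cells, half of them need a baseline bilirubin of 1.5 to 2.0 mg/dL, and the documents give no frequency. Nor is the planned safety analysis undermined: Section 8.6.2 describes adverse events by counts and percentages, and that is unaffected.

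The conclusion rests on the documents alone, with ascites and encephalopathy at 1 point each and the prescribing information unseen.

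**What to change.** - In Arm B, calculate Child-Pugh at each cycle visit during Zepatier dosing and at any hepatic ECI. Use the albumin, bilirubin and PT/INR already drawn, and record ascites and encephalopathy grade. Add the marks to the Section 6.1 flow chart.
- State in Sections 5.2.1.4 and 5.2.1.6 that a confirmed score of 7 or more stops Zepatier. Stop RBV with it, because RBV monotherapy is barred. Let the investigator judge non-hepatic causes, such as an anticoagulant effect on PT. No new hold scheme is needed; if a pause is wanted while the score is repeated, Section 5.2.1.6 already says "If for any reason Zepatier needs to be interrupted it can be interrupted for up to 3 days".
- State that Therapy in the permanent discontinuation criteria of Section 5.2.1.3 includes Zepatier.
- Correct U/mL to U/L in the ALT and AST triggers of Section 7.2.4.2.

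The cost is a short amendment, one calculated field and two examination fields per visit. The 45 to 75 scores are a minimum for full courses, because ECI-triggered and confirmatory scores come on top. An occasional repeat draw will be needed. Subjects stopped early may lower observed SVR12, by up to 6.7 percentage points each.

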# Proprietary Information of MD Anderson

Protocol # 2016-0251

Date: February 24, 2020

65

If for any reason RBV needs to be interrupted (e.g. for safety reasons), if possible, it should be restarted within 3 days.

## 5.2.2 Timing of Dose Administration

Cycle 1 Day 1 treatment with pembrolizumab should begin on the day of allocation, but no later than 3 days from the date the subject is allocated to study treatment. However, every effort should be made to begin trial treatment on the day of allocation.

Trial treatment should be administered on Day 1 of each cycle after all procedures/assessments have been completed as detailed on the Trial Flow Chart (Section 6.0). Trial treatment may be administered up to 3 days before or after the scheduled Day 1 of each cycle due to administrative reasons.

Pembrolizumab 200 mg will be administered as a 30 minute IV infusion Q3W. Sites should make every effort to target infusion timing to be as close to 30 minutes as possible. However, given the variability of infusion pumps from site to site, a window of -5 minutes and +10 minutes is permitted (i.e., infusion time is 30 minutes: -5 min/+10 min).

The Pharmacy Manual contains specific instructions for the preparation of the pembrolizumab infusion fluid and administration of infusion solution.

Pembrolizumab trial treatment will be administered on an outpatient basis.

Subjects will be instructed to take Zepatier orally without regard to food in regimens not requiring RBV. Subjects will be instructed to take Zepatier and RBV (in RBV containing arms) orally, in the morning. RBV should be taken with food. A second daily dose of RBV should be taken by itself, with food, in the evening.

No more than 12 weeks worth of Zepatier/ treatment are to be given and no more than 16 weeks worth of Zepatier/RBV treatment are to be given.

## 5.2.3 Trial Blinding/Masking

This is an open-label trial; therefore, Merck, investigators, and subjects will know the treatment administered.

## 5.3 Randomization or Treatment Allocation

This is a non-randomized trial. Subjects will be allocated per arm based upon inclusion and exclusion criteria. Arms are not compared. All enrolled subjects will be allocated to receive pembrolizumab 200 mg Q3W as monotherapy in an unblinded fashion (Section 2.1).

## 5.4 Stratification

No stratification based on age, sex or other characteristics will be used in this trial

# Proprietary Information of MD Anderson

Protocol # 2016-0251

Date: February 24, 2020

66

## 5.5 Concomitant Medications/Vaccinations (allowed & prohibited)

### 5.5.1 Acceptable Concomitant Medications

All treatments that the Investigator considers necessary for a subject's welfare may be administered at the discretion of the Investigator in keeping with the community standards of medical care. All concomitant medication will be recorded on the CRF including all prescription, over-the-counter (OTC) products, herbal supplements, and IV medications and fluids. If changes occur during the trial period, documentation of drug dosage, frequency, route, and date should also be included on the CRF. All concomitant medications received within 28 days prior to the first dose of trial treatment and up to 30 days after the last dose of trial treatment should be recorded. Concomitant medications administered 30 days after the last dose of trial treatment should be recorded for SAEs and ECIs as defined in Section 7.2.

### 5.5.2 Prohibited Concomitant Medications

Subjects are prohibited from receiving the following therapies during the Screening and Treatment Phase of this trial:

- Antineoplastic systemic chemotherapy or biological therapy
- Immunotherapy not specified in this protocol
- Chemotherapy not specified in this protocol
- Investigational agents other than pembrolizumab
- Radiation therapy

Note: Radiation therapy to a symptomatic solitary lesion or to the brain may be allowed at the Investigator's discretion.

- Live vaccines within 30 days prior to the first dose of trial treatment and while participating in the trial. Examples of live vaccines include, but are not limited to, the following: measles, mumps, rubella, varicella/zoster, yellow fever, rabies, BCG, and typhoid vaccine. Seasonal influenza vaccines for injection are generally killed virus vaccines and are allowed; however, intranasal influenza vaccines (eg, FluMist®) are live attenuated vaccines and are not allowed.
- Systemic glucocorticoids for any purpose other than to modulate symptoms from an ECI that is suspected to have an immunologic etiology. The use of physiologic doses of corticosteroids may be approved after consultation with Merck.
- Chronic use of NSAIDs with a high risk of bleeding, for example, indomethacin, ibuprofen, naproxen, or similar agents. Chronic use of aspirin up to 325 mg/day is permitted.

Subjects who, in the assessment of the Investigator, require the use of any of the aforementioned treatments for clinical management should be removed from the trial. Subjects may receive other medications that the Investigator deems to be medically necessary.

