### 5.2.1.2 Dose Modification and Toxicity Management Guidelines for Pembrolizumab

AEs associated with pembrolizumab exposure may represent an immunologic etiology. These immune-related AEs (irAEs) may occur shortly after the first dose or several months after the last dose of pembrolizumab treatment and may affect more than one body system simultaneously. Therefore, early recognition and initiation of treatment is critical to reduce complications. Based on existing clinical study data, most irAEs were reversible and could be managed with interruptions of pembrolizumab, administration of corticosteroids and/or other supportive care. For suspected irAEs, ensure adequate evaluation to confirm etiology or exclude other causes. Additional procedures or tests such as bronchoscopy, endoscopy, skin biopsy may be included as part of the evaluation. Based on the severity of irAEs, withhold or permanently discontinue pembrolizumab and administer corticosteroids. Dose modification and toxicity management guidelines for irAEs associated with pembrolizumab are provided in Table 6.

Table 6 Dose modification and toxicity management guidelines for immune-related AEs associated with pembrolizumab

General instructions:				
irAEs	Toxicity grade or conditions (NCI CTCAE v4.0)	Action taken to pembrolizumab	irAE management with corticosteroid and/or other therapies	Monitor and follow-up
Pneumonitis	Grade 2	Withhold	
 
Administer corticosteroids (initial dose of 1-2 mg/kg prednisone or equivalent) followed by taper
 
	
 
Monitor subjects for signs and symptoms of pneumonitis
 
Evaluate subjects with suspected pneumonitis with radiographic imaging and initiate corticosteroid treatment
 
Add prophylactic antibiotics for opportunistic infections
 

	Grade 3 or 4, or recurrent grade 2	Permanently discontinue		

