Diarrhea / colitis	Grade 2 or 3	Withhold	
 
Administer corticosteroids (initial dose of 1-2 mg/kg prednisone or equivalent) followed by taper
 
	
 
Monitor subjects for signs and symptoms of enterocolitis (i.e. diarrhea, abdominal pain, blood or mucus in stool with or without fever) and of bowel perforation (i.e. peritoneal signs and ileus).
 
Subjects with <math>\ge</math>Grade 2 diarrhea suspecting colitis should consider GI consultation and performing endoscopy to rule out colitis.
 
Subjects with diarrhea/colitis should be advised to drink liberal quantities of clear fluids. If sufficient oral fluid intake is not feasible, fluid and electrolytes should be substituted via IV infusion.
 

	Grade 4	Permanently discontinue		

General instructions:				

 
1. Corticosteroid taper should be initiated upon AE improving to Grade 1 or less and continue to taper over at least 4 weeks.
 
2. For situations where pembrolizumab has been withheld, pembrolizumab can be resumed after AE has been reduced to Grade 1 or 0 and corticosteroid has been tapered. Pembrolizumab should be permanently discontinued if AE does not resolve within 12 weeks of last dose or corticosteroids cannot be reduced to <math>\leq 10</math> mg prednisone or equivalent per day within 12 weeks.
 
3. For severe and life-threatening irAEs, IV corticosteroid should be initiated first followed by oral steroid. Other immunosuppressive treatment should be initiated if irAEs cannot be controlled by corticosteroids.
 
				
irAEs	Toxicity grade or conditions (NCI CTCAE v4.0)	Action taken to pembrolizumab	irAE management with corticosteroid and/or other therapies	Monitor and follow-up
Type 1 diabetes mellitus (T1DM) or Hyperglycemia	Newly onset T1DM or Grade 3 or 4 hyperglycemia associated with evidence of $\beta$ -cell failure	Withhold	
 
• Initiate insulin replacement therapy for subjects with T1DM
 
• Administer anti-hyperglycemic in subjects with hyperglycemia
 
	
 
• Monitor subjects for hyperglycemia or other signs and symptoms of diabetes.
 

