**General instructions:**

1. Corticosteroid taper should be initiated upon AE improving to Grade 1 or less and continue to taper over at least 4 weeks.
2. For situations where pembrolizumab has been withheld, pembrolizumab can be resumed after AE has been reduced to Grade 1 or 0 and corticosteroid has been tapered. Pembrolizumab should be permanently discontinued if AE does not resolve within 12 weeks of last dose or corticosteroids cannot be reduced to  $\leq 10$  mg prednisone or equivalent per day within 12 weeks.
3. For severe and life-threatening irAEs, IV corticosteroid should be initiated first followed by oral steroid. Other immunosuppressive treatment should be initiated if irAEs cannot be controlled by corticosteroids.

irAEs	Toxicity grade or conditions (NCI CTCAE v4.0)	Action taken to pembrolizumab	irAE management with corticosteroid and/or other therapies	Monitor and follow-up
	Grade 3 or 4	Permanently discontinue	
 
• Administer corticosteroids (prednisone 1-2 mg/kg or equivalent) followed by taper.
 
	
Myocarditis	Grade 1 or 2	Withhold	
 
• Based on severity of AE administer corticosteroids
 
	
 
• Ensure adequate evaluation to confirm etiology or exclude other causes
 

	Grade 3 or 4	Permanently discontinue		
All Other irAEs	Intolerable/persistent Grade 2	Withhold	
 
• Based on severity of AE administer corticosteroids
 
	
 
• Ensure adequate evaluation to confirm etiology or exclude other causes
 

	Grade 3	Withhold or discontinue based on the type of event. Events that require discontinuation include and not limited to: Guillain-Barré Syndrome, encephalitis		
	Grade 4 or recurrent Grade 3	Permanently discontinue		

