## ii. Management

- Interrupt pembrolizumab treatment and alert Merck as per ECI criteria above for ALT, AST, bilirubin, and hepatic decompensation.
- Start IV corticosteroid (methylprednisolone 125 mg) followed by oral corticosteroid (1-2 mg/kg/day).
- Monitor with biweekly laboratory tests including AST, ALT, Tbil, Dbil, ALP, and INR.
- If symptoms and laboratory tests resolve to  $\leq$ Grade 1 or baseline (if abnormal at baseline), taper steroids over 28 days. Pembrolizumab treatment may be restarted after steroid treatment has been tapered to prednisone  $\leq 10$  mg/day (or equivalent dose of another agent). Treatment and laboratory results must be reported on a case report form (CRF).
- If laboratory abnormalities do not resolve within 3 weeks, or steroids cannot be lowered to  $\leq 10$  mg/day (or prednisone equivalent) within 12 weeks, or subjects show evidence of decompensation to CPC status or have esophageal or variceal bleeding at any point, treatment must be permanently discontinued. This must be reported on a CRF.

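### Section 5.5.2 exempts steroids only for immune-cause events of clinical interest, so read literally it removes subjects with non-hepatic immune toxicity whom Table 6 treats and re-doses

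*Combined protocol and SAP*

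**What the plan says.** **Prohibited medication (5.5.2).** The list for the Screening and Treatment Phase includes "Systemic glucocorticoids for any purpose other than to modulate symptoms from an ECI that is suspected to have an immunologic etiology". The only other allowance is physiologic doses after consultation with Merck. Subjects who, in the investigator's assessment, "require the use of any of the aforementioned treatments for clinical management should be removed from the trial".

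**Events of clinical interest (7.2.4.2).** The list has overdose without symptoms, hepatic laboratory changes and hepatic decompensation, and reactivation of HBV or HCV. No pneumonitis, colitis or myocarditis appears in it.

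**Toxicity management (5.2.1.2, Table 6).** Pembrolizumab is withheld for Grade 2 pneumonitis and for Grade 2 or 3 diarrhea/colitis, and both rows say: "Administer corticosteroids (initial dose of 1-2 mg/kg prednisone or equivalent) followed by taper". For Grade 1-2 myocarditis, and for intolerable or persistent Grade 2 events among other irAEs, the drug is also withheld and the instruction is "Based on severity of AE administer corticosteroids". The general instructions start the taper once the event has improved to Grade 1 or less and "continue to taper over at least 4 weeks". After that, "pembrolizumab can be resumed after AE has been reduced to Grade 1 or 0 and corticosteroid has been tapered". Permanent discontinuation applies if the steroid cannot be brought down to 10 "mg prednisone or equivalent per day within 12 weeks".

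**Arm B (5.5.3, 5.2.1.6).** Section 5.5.3 does not permit systemic corticosteroids at 10 mg/day prednisone equivalent or more, except rapid tapers lasting less than 1 week. Section 5.2.1.6 keeps the subject on Zepatier when pembrolizumab is interrupted, unless the cause is severe liver toxicity. It asks for consultation with Merck if Zepatier is interrupted for more than 3 days.

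**The concern.** Immune toxicity that needs steroids is foreseeable with pembrolizumab, and Table 6 was written for it. For a non-hepatic event at a withhold grade, Table 6 says to treat, taper and resume. Section 5.5.2 says that a subject who needs that same steroid leaves the trial. The cause appears to be one term: the exemption is tied to the ECI list, while the toxicity table covers irAEs generally.

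The first thing at stake is patient management, because a subject who has recovered could lose pembrolizumab that the protocol otherwise allows. Tolerability is a primary objective in both arms, so what happens after such an event matters. In Arm B the investigator also meets a second steroid limit without an immune-toxicity exception, at a time when Zepatier is meant to continue.

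**Working it through.** The plan states no figure on this point, so the check is a comparison of sections plus simple dose arithmetic.

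**Step 1. Which steroid uses fall outside the 5.5.2 exemption?**

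- Grade 2 pneumonitis and Grade 2-3 diarrhea/colitis: withheld, 1-2 mg/kg, not an ECI. Outside the exemption, with re-dosing allowed by Table 6. These are the clear cases.
- Grade 1-2 myocarditis and persistent Grade 2 other irAEs: withheld, steroid by severity, not an ECI. Outside the exemption whenever the dose is above physiologic.
- Hypophysitis: steroids as clinically indicated. These might fit the physiologic-dose allowance.
- Type 1 diabetes and thyroid events: Table 6 directs no corticosteroid, so they are not affected.
- Immune-related hepatitis (5.2.1.3): the triggering laboratory changes are ECIs, so 5.5.2 permits the steroid.
- Grades at which Table 6 stops pembrolizumab permanently: no conflict over re-dosing.

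**Step 2. Could the physiologic-dose allowance, or the Arm B limit, cover the Table 6 regimen?** Body weight is assumed to be 50-100 kg, because the documents give no distribution.

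- Lowest starting dose: 50 kg × 1 mg/kg = 50 mg/day. Highest: 100 kg × 2 mg/kg = 200 mg/day.
- Against the 10 mg/day limit in 5.5.3: 50/10 = 5 and 200/10 = 20.
- Taper length: at least 4 weeks = 28 days, against an exception of under 7 days; 28/7 = 4.
- If the taper is linear over 28 days (an assumption), days at or above 10 mg/day = 28 × (1 − 10/start). From 50 mg/day this is 28 × 0.80 = 22.4 days. From 200 mg/day it is 28 × 0.95 = 26.6 days.

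The documents give no number for a physiologic dose. A starting dose of 50-200 mg/day is well above one, and neither exception reaches it.

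**Step 3. Can the steroid course overlap Zepatier?** Zepatier runs for 12 or 16 weeks. A 4-week taper lies wholly inside dosing if it starts by week 12 − 4 = 8, or week 16 − 4 = 12. Overlap is therefore possible for much of the Zepatier course.

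**Step 4. What does each removal cost?** With about 15 subjects per arm and no replacement (5.7), one subject is 1/15 = 6.7% of an arm. The documents give no overall rate of steroid-treated irAEs, so an expected number cannot be calculated.

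**The case against.** The strongest reply is that Table 6 is the specific instruction and the removal sentence in 5.5.2 is a general *should*. Section 5.5.1 allows any treatment needed for the subject's welfare, and the Supportive Care Guidelines in 5.6 repeat the steroid advice. This disposes of one tempting reading, that the plan denies steroids to a subject who needs them. It does not say whether that subject may be re-dosed. Even if leaving the trial is taken to mean only stopping study treatment, it still blocks the resumption that Table 6 allows.

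The second reply concerns follow-up. The section headed Discontinuation of Treatment says that stopping treatment is not withdrawal from the study, and 7.1.5.1 and 8.13.3 encourage continued follow-up. That stands. A reader might infer that SVR12 results will be lost and coded as failures, but this needs several steps:

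- The removal sentence must be put ahead of those three sections.
- The event must come before the SVR12 sample, at about week 12 + 12 = 24 or 16 + 12 = 28. Pembrolizumab can run for about 2 years, so later events cannot affect it.
- The missing value must be coded as failure. Section 8.13.3 treats treatment-related discontinuation as failure, but puts protocol violation and administrative reasons in another class. That class is excluded under one approach and failed under the other, and the section does not say which approach is primary.

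The third reply is that Arm B is not without a procedure. Section 5.5.3 says that discontinuing trial therapy may be required when a drug prohibited by the exclusion criteria is indicated. It refers questions to Merck's clinical director, and makes continuation a joint decision of investigator, Merck and subject. The 3 days in 5.2.1.6 trigger consultation and are not a cap. Section 5.2.1.4 restricts dose modification, while interruption is governed separately. These points stand. What is left is that a predictable event is settled case by case, against a limit that the protocol's own toxicity table requires the investigator to exceed.

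**Conclusion.** The contradiction is in the text and should be corrected. Read literally, 5.5.2 removes subjects with steroid-treated, non-hepatic irAEs at withhold grades, and Table 6 re-doses the same subjects. The main consequence is wrongful loss of pembrolizumab re-dosing. In Arm B the 5.5.3 limit has the same missing exception, and it is exceeded 5- to 20-fold at the Table 6 starting dose under the 50-100 kg assumption.

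The size in subjects is unknown. A reader might also infer that the tolerability analysis loses its denominator. It does not: the triggering event is still reported under 7.2.1, and a treated subject stays in the all-subjects-as-treated population (8.5.2). Later safety, imaging and survival data, and SVR12, are at risk only if the removal sentence is followed over the sections that keep subjects in follow-up.

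**What to change.** 1. In 5.5.2, tie the steroid exemption to any AE of suspected immunologic etiology managed under Table 6 or Section 5.2.1.3, in place of ECIs. Table 7 need not be named to resolve the re-dosing conflict, because it lists corticosteroids only for Grade 3-4 infusion reactions, after which pembrolizumab is stopped for good.
2. In the same section, state that subjects who need a prohibited therapy discontinue study treatment but stay in follow-up. This would apply to every therapy on the list. Cite the section by its heading, Discontinuation of Treatment, because three sections carry the number 5.6.2.
3. In 5.5.3, add the same immune-toxicity exception to the 10 mg/day limit. Zepatier is then maintained under the existing rule in 5.2.1.6, unless there is severe liver toxicity.

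The cost is amendment wording in two sections. No new data, visits or subjects are needed.
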